**Table 1 Summary of Changes (Version 4)**

Changes in Version 4	Rationale

Section 5.4 Efficacy Analyses and Section 7 Changes to Planned Analyses
 
Revised the primary and secondary analyses to utilize MMRM for the primary analysis for non-EMA registration and have separate analyses for EMA registration.
	
These changes have been made due to correspondence with the FDA, separate analyses will be performed for the different registrations for the non-EMA and EMA. The supplementary analyses have been reduced to allow for clearer interpretation of the co-primary analyses.

**Table 2 Summary of Changes (Version 3)**

Changes in Version 3	Rationale

Sections 3.1.2, 5.1.2 and 5.4.2. Revised the order of the secondary efficacy objectives, endpoints and analyses.
	
To enable the secondary endpoints to be part of the statistical hierarchy of testing

Section 5.2.3 Protocol Deviations. Removed restricted medications criteria. Added criteria relating to exclusion criteria 6.
	
Due to blinded data review, it was found the assumption that the restricted medications would improve efficacy were incorrect, this is investigated in sensitivity analyses only.
 
As per Exclusion Criteria 6, Geriatric Depression Scale (GDS) greater than 8, may affect efficacy.

Section 5.4.1 Primary Efficacy Analysis. Co-primary Analysis of Change from Baseline in the MoCA Total Score at 12 Weeks. Further define MAR and MNAR for the MoCA analysis.
	
For clarification purposes.

Section 5.4.1 Primary Efficacy Analysis, Section 5.4.2 Secondary Efficacy Analysis, Section 5.4.3 Exploratory Efficacy Analysis. Changes to censoring on restricted medications, removed from all and add as a sensitivity analysis on co-primaries only.
	
Due to blinded data review, it was found the assumption that the restricted medications would improve efficacy were incorrect, therefore the censoring of this data is moved to sensitivity analyses only.

**Table 3 Summary of Changes (Version 2)**

Changes in Version 2	Rationale
Throughout the document: Editorial corrections are made to correct typos	For clarification purposes.
Throughout the document: based on Protocol Version 4, the addition of memantine	Added subgroup analyses for memantine use.
Section 4 “Sample Size” additional information on current sample size and study data	The clinical meaningful treatment difference and SD for MoCA total score assumptions have been updated based on partial blinded study data.
Section 5.2.2 “Subject Disposition”	Wording added to summarize overall and by stratification factors.
Section 5.2.4 “Demographic and Other Baseline Characteristics”	Added further variables to be summarized.
Section 5.4.1 “Co-primary Analysis of the CIBIC-Plus Scale at 12 Weeks”. Edited regarding censoring of AChEI and non-AChEI restricted medications  “Table 4: Primary Efficacy Analyses” added.	Co-primary Analysis of the CIBIC-Plus Scale at 12 Weeks edited to add that changes in both AChEI and non-AChEI restricted medications will be censored. This is due to what CIBIC-Plus measures and maybe affected by changes in any of these medications.  Table added to describe all of the primary, sensitivity and supplementary analyses.
Section 5.4.2 and 5.4.3 “Secondary and Exploratory Efficacy Analyses”  “Table 5: Secondary Efficacy Analyses” added.	Clarification and additional analyses added regarding the censoring of changes in AChEI medications and censoring of both AChEI and non-AChEI restricted medications.  Table added to describe all the secondary analyses.
Section 5.6.5 “Electrocardiograms”	Further abnormal ECGs summary added.
Section 5.6.6.2 “UPDRS-III”	Added summary censoring data after changes in DLB medication.
Section 5.7 “Other Analyses”	Detail added for censoring of data based on medication changes.

**Table 3 Summary of Changes (Version 2)**

Changes in Version 2	Rationale
Section 6 “Interim Analysis”, deleted.	Removed to coincide with decision to not do the adhoc futility analysis as per protocol amendment 03.
Section 8.1.2 “ Treatment Duration for Efficacy Analyses”.	Clarification for windowing
Section 8.1.4 “Censoring of Efficacy Data Based on Changes in Medications” added.	Added section to describe extra analyses and descriptions of censoring
Section 8.2.2 “Treatment Duration for Safety Analyses” added wording regarding treatment emergence.	Clarification regarding the definition of treatment emergent and windowing.
Section 8.2.4 “Safety Data Collected after the ED Visit”	Clarification given that separate ED visits will not be produced for the safety data, only treatment emergent data will be windowed as appropriate.
Section 8.4 “Algorithms for Safety Parameters” added	UPDRS-III subscore derivations added.

## 2 LIST OF ABBREVIATIONS AND DEFINITIONS OF TERMS

Abbreviation	Term
AChEI	Acetylcholinesterase inhibitors
AE	Adverse event
ANCOVA	Analysis of covariance
ANOVA	Analysis of variance
ATC	Anatomical Therapeutic Chemical
BMI	Body mass index
C-CASA	Columbia- classification algorithm of suicide assessment
CFI	Cognitive Fluctuation Inventory
CGIC-DLB	Clinician Global Impression of Change in Dementia with Lewy Bodies
cGMP	Cyclic guanosine monophosphate
CI	Confidence interval
CIBIC-Plus	Clinician's Interview Based Impression of Change Plus Caregiver Input
CRF	Case report form
CSF	Cerebrospinal fluid
CSR	Clinical study report
C-SSRS	Columbia – Suicide Severity Rating Scale
CV	Coefficient of variation
DEMQOL	Dementia Quality of Life Measure
DEMQOL-Proxy	Dementia Quality of Life Measure by Proxy
DLB	Dementia with Lewy bodies
DMC	Data monitoring committee
DSMB	Data safety monitoring board
ECG	Electrocardiography
eCRF	Electronic case report form
ED	Early Discontinuation
EEG	Electroencephalography

EQ VAS	Overall health rating of EQ-5D
EQ-5D	EuroQol-5 Dimension questionnaire
EQ-5D Proxy	EuroQol-5 Dimension questionnaire by Proxy
FAS	Full analysis set
GDS	Geriatric Depression Scale
GLMM	Generalized linear mixed models
IA	Interim Analysis
ITT	Intent to treat
LP	Lumbar puncture
LS	Least squares
MAR	Missing at random
MCMC	Markov Chain Monte Carlo
MedDRA	Medical Dictionary for Regulatory Activities
MI	Multiple imputation
MMRM	Mixed-effects models for repeated measures
MMSE	Mini Mental State Examination
MNAR	Missing not at random
MoCA	Montreal Cognitive Assessment
NPI	Neuropsychiatric Inventory
PD	Pharmacodynamic
PGx	Pharmacogenomic
PK	Pharmacokinetic
PP	Per protocol
PT	Preferred term
QALYs	Quality-adjusted life years
QD	Once daily
QoL	Quality of Life
SAE	Serious adverse event
SAP	Statistical analysis plan
SAS	Statistical analysis system

SCOPA-Sleep	Scales for Outcome in Parkinson's disease-Sleep
SD	Standard deviation
SE	Standard error
SI	Système International
SOC	System organ class
TEAE	Treatment-emergent adverse event
TEMAV	Treatment-emergent markedly abnormal laboratory
TLG	Tables, listings, and graphs
UPDRS-III	Unified Parkinson Disease Rating Scale - III
WHO	World Health Organization
WHO DD	World Health Organization Drug Dictionary

### 3 INTRODUCTION

The purpose of this statistical analysis plan (SAP) is to describe the procedures and the statistical methods that will be used to analyze and report results based on clinical database for the Eisai Protocol E2027-G000-201. PK/PD/PGx analysis and relevant endpoints will not be described in this SAP but will be described in separate PK/PD/PGx analysis plans.

#### 3.1 Study Objectives

##### 3.1.1 Primary Objectives

To determine whether E2027 is superior to placebo on the cognitive endpoint of Montreal Cognitive Assessment (MoCA) in subjects with dementia with Lewy bodies (DLB) after 12 weeks of treatment

To determine whether E2027 is superior to placebo on the global clinical endpoint of Clinician's Interview Based Impression of Change Plus Caregiver Input (CIBIC-Plus) after 12 weeks of treatment

##### 3.1.2 Secondary Objectives

1. To determine whether E2027 is superior to placebo on the following secondary endpoints after 12 weeks of treatment:
  - 1.1. Clinician Global Impression of Change in Dementia with Lewy Bodies (CGIC-DLB)
  - 1.2. Cognitive Fluctuation Inventory (CFI)
  - 1.3. Mini-Mental State Examination (MMSE)
  - 1.4. Neuropsychiatric Inventory (NPI)
2. To evaluate the safety and tolerability of E2027 in subjects with DLB
3. To characterize the population pharmacokinetics (PPK) of E2027 in subjects with DLB, including evaluation of the effects of intrinsic and extrinsic factors on E2027 PK

##### 3.1.3 Exploratory Objectives

1. To explore the efficacy of E2027 compared to placebo on the following endpoints after 12 weeks of treatment:
  - 1.1. Scales for Outcome in Parkinson's disease-Sleep (SCOPA-Sleep)

- 1.2. Dementia-related quality of life as assessed by the Dementia Quality of Life Measure (DEMQOL; interview of subject) and Dementia Quality of Life Measure by Proxy (DEMQOL-Proxy; interview of caregiver or informant about subject)
- 1.3. General health status as assessed by the EuroQol-5 Dimension questionnaire (EQ-5D; completed by subject) and EuroQol-5 Dimensions questionnaire by Proxy Version 1 (EQ 5D Proxy; caregiver or informant completion of report about subject)

To evaluate the relationship between PK exposure of E2027 and its effects on various efficacy and safety endpoints

To explore the PK/pharmacodynamic (PD) relationship between the exposure of E2027 in cerebrospinal fluid (CSF)/plasma and its effects on CSF PD biomarker endpoints, including CSF cyclic guanosine monophosphate (cGMP), if data permit

To explore the relationship between the E2027 PD effects (including CSF cGMP) with E2027 effects on various efficacy endpoints, if data permit

To explore collected pharmacogenomic (PGx) samples by investigating heterogeneity in clinical features of disease, including differences in baseline characteristics as well as response to compound (efficacy, safety and/or absorption, distribution, metabolism, and excretion [ADME]). These exploratory analyses are not limited to this protocol or project. These findings may be used for identification and validation of new drug targets

### 3.2 Overall Study Design and Plan

This is a multicentre, randomized, double-blind, placebo-controlled, parallel-group study in subjects with DLB who will be treated with placebo or E2027 (50 mg once daily [QD]) for 12 weeks.

In some of the countries selected for this study, donepezil is approved for DLB and acetylcholinesterase inhibitors (AChEIs) are often used as part of standard care in patients with DLB. Therefore, the study design allows for add-on therapy to standard of care for DLB, which includes AChEI and/or memantine at stable doses, except for any prohibited medications specified in this protocol. Subjects who are not receiving AChEI or memantine are also eligible, but are not permitted to start such medications during the study. Randomization will be stratified based on whether subjects are on a stabilized dose of AChEI or not and by geographical region (ie, North America, Europe, or Japan). Subjects will be randomly assigned to placebo or E2027 (50 mg QD) in a ratio of 1:1

For all subjects, study participation will comprise 2 phases: Prerandomization and Randomization. The Prerandomization Phase will last for up to 6 weeks and will include a

Screening Period (up to 5 weeks) and a Baseline Period (1 week). The Randomization Phase will last for 16 weeks and will include a Treatment Period (12 weeks) and a Follow-up Period (4 weeks).

Screening will occur between Day -42 and Day -8. The purpose of the Screening Period is to obtain informed consent and to establish protocol eligibility. Eligibility assessments at Screening will be conducted in tiers and subjects will need to satisfy eligibility criteria in each tier before proceeding to the next tier. There are total 6 tiers. Subjects who are deemed eligible after passing all tiers at Screening will proceed to the Baseline Visit.

The baseline visit may take place at any time up to 7 days before the first dose of study drug (Day 1, ie, during Day -7 to Day -1, but should take place at least 2 weeks after the Screening Visit Tier 2 assessments).

After completing study assessments at the Baseline Visit, subjects who continue to be eligible will proceed to the Randomization Phase, and will be randomly assigned to placebo or E2027 (50 mg QD). They will be provided with study drug (placebo or E2027) to start administration in the morning of Day 1 at home. They will continue to take study drug for 12 weeks. During the Treatment Period study visits will be conducted after 2, 4, 6, 9 and 12 weeks on study drug. Safety assessments will be conducted at all these visits. Efficacy assessments will be performed after 6 and 12 weeks on study drug and should be performed at approximately the same time of the day as at the Baseline Visit whenever possible (preferably in the morning).

After the Treatment Period, subjects will complete a Follow-Up Visit 4 weeks after the final dose of study drug.

The end of study was the date of the last study visit for the last subject.

### Early Discontinuation

Subjects who prematurely discontinue study drug for any reason will undergo an Early Discontinuation (ED) Visit within 7 days of their final dose of study drug. The safety and efficacy assessments normally performed after 12 weeks of treatment will be conducted at the ED Visit. In addition, subjects who discontinue study drug are expected to continue in the study for the originally scheduled visits, starting with next such visit that is >7 days after the ED Visit. Subjects who prematurely discontinue the study should attend at least 1 originally scheduled visit after the ED Visit.

### CSF Substudy

A subset of subjects will participate in a substudy in which CSF will be collected by lumbar puncture (LP) during Screening and again during the Randomization Phase after 9 weeks of treatment on study drug. Participation in the substudy will be voluntary. After they have completed all screening assessments and are deemed eligible for the study, a baseline CSF sample will be collected at least 7 days before the Baseline Visit. After they have completed

9 weeks of treatment, they will have a 2nd CSF sample collected. The CSF samples will be collected in the morning at approximately the same time, either in the fasted state (preferred) or at least 2 hours after breakfast.

As data permit, CSF cGMP will be assayed to evaluate the PD effects of E2027 in these subjects with DLB. Other CSF PD biomarkers related to DLB or E2027 PD effects may also be assayed if appropriate. CSF E2027 concentrations will also be determined.

#### Data Safety Monitoring Board

An independent data safety monitoring board (DSMB) will convene at regular intervals to monitor the overall safety of the study and to make recommendations to the sponsor related to study safety as appropriate. The DSMB will be asked to review the cumulative safety data up to the date identified to make a determination if the study is safe to proceed unchanged or to provide recommendations to the sponsor as to how to proceed. The study will proceed, including randomization of additional subjects, during DSMB safety reviews. Details will be provided in the DSMB Charter.

## **4 DETERMINATION OF SAMPLE SIZE**

The MoCA scale was assessed in DLB subjects and reported by Biundo et al. (2016). The observed mean change from baseline in the MoCA total score at 1 year in this report is -1.04 points and the corresponding standard deviation (SD) is 1.32 points. An estimation of the mean change from baseline in the MoCA total score at 3 months is approximately -0.26 points using linear interpolation. It is assumed that E2027 would improve the MoCA total score as compared with baseline and achieve a mean treatment difference of approximately 0.6 points between E2027 and placebo at 12 weeks. The SD of change from baseline in the MoCA total score at 3 months is expected to be smaller than that at 1 year. A conservative estimate of the SD of change from baseline in the MoCA total score is 1.3 points at 12 weeks.

In a 12-week donepezil monotherapy study in subjects with DLB (E2020-J081-431), the estimated proportional odds ratio based on the CIBIC-Plus scale for donepezil 10 mg relative to placebo was 6.14. It is assumed that E2027 would achieve a proportional odds ratio of 2.607 relative to placebo (ie, 42% of the effect size observed in the above donepezil study).

With 80 subjects completing per arm (for 91 randomized subjects per arm, assuming a 12% dropout rate), this study will have approximately 80% power to detect the above effect sizes (ie, mean treatment difference of approximately 0.6 points based MoCA total score and proportional odds ratio of 2.607 based on CIBIC-Plus scale for E2027 relative to placebo) in both co-primary endpoints simultaneously. Therefore, the total sample size of 182 randomized subjects is planned, assuming a 12% dropout rate.

The MoCA total score on blinded study data shows SD is 3 points, to keep 80% power and the effect size of 0.46 with 80 subjects completing each arm, the treatment difference would need to be 1.4. A treatment difference of 1.4 has been shown with blinded study data to be similar to a one unit change in CIBIC-Plus, which is clinically meaningful.

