REVISION HISTORY

Revisions to Version 5.0		
New version/date: Version 6.0/03 Jan 2020 (per Amendment 05)		
Change	Rationale	Affected Protocol Sections
Added results of nonclinical toxicology study.	New nonclinical toxicology findings	Section 7.1.1.3 Section 7.2.2
Added requirement for males subjects to use highly effective contraception and requirement to report pregnancy in female partners of male subjects.	New nonclinical toxicology findings	Section 9.4.7.3 Section 9.5.4.2 Section 9.5.5
Revised the order of the secondary efficacy endpoints.	To enable the secondary endpoints to be part of the statistical hierarchy of testing so that this study can be used in the NDA as one of the pivotal studies	Synopsis 
 • Objectives • Study Endpoints Section 8.2 Section 9.7.1.1.2

Revisions to Version 4.0		
New version/date: Version 5.0/03 Sep 2019 (per Amendment 04)		
Change	Rationale	Affected Protocol Sections
Specified the percentage of randomized subjects who will be on memantine.	To comply with the EU Voluntary Harmonisation Procedure requirement for approval	Synopsis 
 • Study Design Section 7.2.1 Section 9.1

Revisions to Version 3.0		
New version/date: Version 4.0/10 Jul 2019 (per Amendment 03)		
Change	Rationale	Affected Protocol Sections
Removed restriction on the use of memantine prior to and during study participation.	Use of memantine is increasingly more common in patients with dementia with Lewy bodies (DLB) based on ongoing surveys with investigators, and it is also explicitly cited in some national treatment guidelines for DLB (eg, UK National Institute for Health and Care Excellence [2018]).	
Synopsis
 
 • Study Design • Inclusion Criteria • Concomitant Drug/Therapy • Statistical Methods – Efficacy Analyses 
Section 7.1.1 Section 7.2.1 Section 9.1 Section 9.2 Section 9.3.1 Section 9.4.7.2 Section 9.5.1.2.1 Section 9.5.5 Section 9.7.1.4 Section 9.7.1.6.1 Section 9.7.1.8.2 Section 10

Removed ad hoc futility analysis	This was always considered optional and only to be performed if necessary. Moreover, ongoing review of variability data in the efficacy endpoints indicated that such a futility analysis would have high risk of a false negative conclusion on efficacy. Therefore, it will not be conducted.	
Synopsis
 
 • Interim Analyses 
Section 9.7.3

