There are 2 coprimary endpoints which include a cognitive endpoint and a global clinical endpoint as recommended by regulatory guidelines for clinical trials on dementia. The primary endpoint on cognition is the MoCA, which is a composite cognitive endpoint evaluating various domains including attention, memory, executive function and visuospatial abilities. It has greater emphasis on executive functions, attention and visuospatial abilities known to be impaired in DLB and PDD (Biundo, et al., 2016) than MMSE. MoCA is less likely to show ceiling effect and is more sensitive in detecting early cognitive change in DLB than MMSE (Biundo et al., 2016). It showed similar rate of cognitive decline with MMSE in 1-year follow-up of DLB patients (Biundo et al., 2016). Moreover, it showed treatment benefit on cognition in a clinical trial of rivastigmine in PDD, indicating sensitivity to treatment effects of cognitive enhancing drugs (Li, et al., 2015). The coprimary endpoint on global clinical status is the CIBIC-Plus which evaluates global clinical impression of change from baseline by an independent rater who determines change in clinical status solely based on interview with the subject and caregiver or informant without reviewing efficacy and safety data obtained postrandomization. It showed overall clinical benefit in subjects treated with donepezil with PDD (Dubois, et al., 2012) and DLB (Mori, et al., 2012). The use of both coprimary endpoints (one on cognition and one on global clinical status) is consistent with regulatory guidelines for clinical trials in dementia such that if E2027 shows positive results on both coprimary endpoints, the study may be considered as a pivotal study in future regulatory submissions. Thus, in this study E2027 (50 mg QD) has to show statistically significant benefit on both the MoCA and the CIBIC-Plus for E2027 compared to placebo. If this is not achieved, but E2027 (50 mg QD) shows statistically significant benefit on at least the MoCA, then the result is considered positive for POC, but not a positive pivotal study, and additional pivotal studies will be conducted.

Other cognitive endpoints, including MMSE and CFI, are secondary endpoints. The MMSE is commonly used in clinical practice to document subjects' cognitive status and showed efficacy with donepezil in PDD (Dubois, et al., 2012) and DLB (Mori, et al., 2012; Ikeda, et

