9.7.2 Determination of Sample Size

The MoCA scale was assessed in DLB subjects and reported in [Biundo et al. \(2016\)](#). The observed mean change from baseline in the MoCA total score at 1 year in this report is -1.04 points and the corresponding standard deviation (SD) is 1.32 points. An estimation of the mean change from baseline in the MoCA total score at 3 months is approximately -0.26 points using linear interpolation. It is assumed that E2027 would improve the MoCA total score as compared with baseline and achieve a mean treatment difference of approximately 0.6 points between E2027 and placebo at 12 weeks. The SD of change from baseline in the MoCA total score at 3 months is expected to be smaller than that at 1 year. A conservative estimate of the SD of change from baseline in the MoCA total score is 1.3 points at 12 weeks.

In a 12-week donepezil monotherapy study in subjects with DLB (E2020-J081-431), the estimated proportional odds ratio based CIBIC-Plus scale for donepezil 10 mg relative to placebo was 6.14. It is assumed that E2027 would achieve a proportional odds ratio of 2.607 relative to placebo (ie, 42% of the effect size observed in the above donepezil study).

With 80 subjects completing per arm (for 91 randomized subjects per arm, assuming a 12% dropout rate), this study will have approximately 80% power to detect the above effect sizes (ie, mean treatment difference of approximately 0.6 points based MoCA total score and proportional odds ratio of 2.607 based on CIBIC-Plus scale for E2027 relative to placebo) in both coprimary endpoints simultaneously. Therefore, the total sample size of 182 randomized subjects is planned, assuming a 12% dropouts rate.

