## **5 STATISTICAL METHODS**

All statistical tests will be 2-sided at the 5% significance level unless otherwise stated. All descriptive statistics for continuous variables will be reported using mean, standard deviation (SD), median, minimum, maximum and number of subjects with non-missing data. Categorical variables will be summarized as number (percentage) of subjects.

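### The 80% power statement for a 0.6-point MoCA difference still stands, although at the blinded SD of 3 (if that is the SD of change) MoCA power is about 24%

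*SAP*

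**What the plan says.** The sample-size text is the same in the protocol synopsis, Protocol 9.7.2 and SAP 4. It assumes a MoCA difference of 0.6 points at 12 weeks and a CIBIC-Plus proportional odds ratio of 2.607. On variability it says "A conservative estimate of the SD of change from baseline in the MoCA total score is 1.3 points at 12 weeks". With 80 completers per arm (91 randomized, 12% dropout) it concludes that "this study will have approximately 80% power to detect the above effect sizes", on both co-primary endpoints together.

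SAP 4 alone goes on: "The MoCA total score on blinded study data shows SD is 3 points", and "to keep 80% power and the effect size of 0.46 with 80 subjects completing each arm, the treatment difference would need to be 1.4". The SAP change table for Version 2 describes this as a revision: "The clinical meaningful treatment difference and SD for MoCA total score assumptions have been updated based on partial blinded study data".

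The protocol carries no matching change. Amendment 03 dropped the ad hoc futility analysis partly because "ongoing review of variability data in the efficacy endpoints indicated that such a futility analysis would have high risk of a false negative conclusion". None of Amendments 03, 04 or 05 lists Section 9.7.2 among the affected sections.

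Success requires a significant result on both co-primary endpoints (SAP 5.3.3). Protocol 9.2 adds that if the joint criterion fails but E2027 "shows statistically significant benefit on at least the MoCA, then the result is considered positive for POC".

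**The concern.** SAP 4 holds two power statements for the same 80 completers per arm: about 80% for 0.6 points, and 80% only if the difference is 1.4. Nothing says which one governs. The protocol holds only the first, so someone reading the protocol alone would believe that the trial can detect 0.6 MoCA points, jointly with CIBIC-Plus, with about 80% power.

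The SAP also leaves unclear what the SD of 3 measures. Its other MoCA SDs are of change from baseline, but this sentence names the total score.

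MoCA decides two claims, the joint co-primary claim and proof of concept on MoCA alone. A reader who trusts the 80% figure would take a non-significant MoCA result as evidence against a 0.6-point effect. At an SD of change of 3 the data could not support that reading.

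**Working it through.** **Inputs.** 80 completers per arm, 1:1 allocation; differences 0.6 and 1.4; SDs 1.3 and 3 (all SAP 4). For the tests, "All statistical tests will be 2-sided at the 5% significance level unless otherwise stated" (SAP 5).

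**Formula.** Two-sample t-test, noncentral t with 158 degrees of freedom. The standard error is SD × √(2/80) = SD × 0.1581, and the noncentrality is the difference divided by the standard error.

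| Difference | SD of change | Difference/SD | Noncentrality | Power |
|---|---|---|---|---|
| 0.6 | 1.3 | 0.46 | 2.92 | 82.7% |
| 0.6 | 3 | 0.20 | 1.26 | 24.2% |
| 1.4 | 3 | 0.47 | 2.95 | 83.5% |

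**The plan's own figure.** The first row is the MoCA part of the planned power. The documents give no CIBIC-Plus category distribution, so joint power can only be bracketed. Four assumed distributions give CIBIC-Plus power of 89% to 93%. Joint power is then 74% to 77% if the two tests are independent, and about 79% to 81% with CIBIC-Plus power of 93% and correlation 0.3 to 0.7. That is consistent with approximately 80%. Dropout also checks: 80/0.88 = 90.9, so 91 per arm. The SAP's revised difference checks too: 0.46 × 3 = 1.38, given as 1.4; the smallest difference with 80% MoCA power at SD 3 is 1.34.

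**Power for 0.6 points at SD 3.** The second row gives 24%. With all 91 per arm it would be 27%. Joint power cannot exceed the MoCA power; under the same assumed CIBIC-Plus powers and correlations it is 22% to 24%.

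**What 80% power for 0.6 points would take.**
- At 80 per arm, an SD of change of at most 1.35.
- At SD 3, by the normal formula, 2 × (1.960 + 0.842)² × 3²/0.6² = 393 completers per arm. The same formula at SD 1.3 gives 74.

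**Precision at SD 3.** The 95% CI half-width is 1.975 × 3 × 0.1581 = 0.94 points. A CI centred on zero excludes 0.6 only if the SD is below 0.6/(1.975 × 0.1581) = 1.92.

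**Blinded pooling.** A pooled SD also contains any treatment difference. If the true difference were 1.4, the within-arm SD would be √(9 − 1.4²/4) = 2.92 and power for 0.6 points 25%. The conclusion does not change.

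**If 3 is instead the SD of the raw score.** Assume equal SDs at baseline and week 12 with correlation r (not in the documents). The SD of change is then 3 × √(2(1 − r)).

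| r (assumed) | SD of change | Power for 0.6 |
|---|---|---|
| 0.5 | 3.00 | 24% |
| 0.7 | 2.32 | 37% |
| 0.8 | 1.90 | 51% |
| 0.9 | 1.34 | 80% |

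**Baseline adjustment.** The planned MMRM includes baseline MoCA, and the documents give no residual SD. As illustrations only, residual SDs of 2.5 or 2 would give 33% or 47% for 0.6 points.

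**The case against.** The strongest reply is that the SAP already discloses the loss. Immediately after the 80% sentence it reports SD 3 and says that 1.4 points are needed, and the change table says that the assumptions were updated. The retained sentence is conditional on its stated inputs, reproduces on them, and records why 182 subjects were chosen. Protocol 9.7 and 9.7.1 send statistical detail to the SAP. The reason given in Amendment 03 names neither MoCA nor an SD. The 24% comes from an unadjusted t-test, not from the planned MMRM. Finally, the objective is superiority, so excluding 0.6 points is not a goal of the plan.

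Much of this stands. The SAP conceals nothing, the original planning arithmetic is sound, and the futility rationale does not by itself show that Section 9.7.2 had to change then. The CI width bears on how a null result is read, not on the success rule.

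It does not settle the matter. SAP 4 still carries both statements without ranking them, and no section gives the power for 0.6 points at SD 3. The protocol is silent on the update. Baseline adjustment could help, but even an assumed residual SD of 2 leaves power at 47%. That the SD label can be inferred from the SAP's own effect-size step is a reason to write it down.

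**Conclusion.** The concern holds and should be fixed. As a current statement, about 80% power for 0.6 MoCA points is not supported by the variability that the SAP itself reports. If the SD of 3 is the SD of change, MoCA power for 0.6 points is about 24%, and power for both co-primary endpoints is no higher.

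This rests on 80 completers per arm, a two-sided t-test at 0.05, and reading the 3 as an SD of change. The SAP's own step supports that reading: it keeps the effect size of 0.46 (0.6/1.3, where 1.3 is an SD of change) and sets 3 in place of 1.3. The sentence does not say so, however, and under the raw-score reading the figure could lie anywhere from 24% to 80% over the assumed correlations of 0.5 to 0.9. The defect lies in the stated power and its labelling; the design and the analysis are not put in question.

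**What to change.** In SAP 4:

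- Label the 0.6-point difference and SD 1.3 as the original planning assumption, replaced by 1.4 points and SD 3.
- State whether 3 is the SD of change from baseline. If it is, add: *With 80 completers per arm and an SD of change of 3, MoCA power for a 0.6-point difference is about 24% (two-sided t-test, alpha 0.05, without baseline adjustment), and power for both co-primary endpoints is no higher.* If it is not, give the SD of change and recompute.
- Add one line: *This section replaces the power statement in Protocol 9.7.2 and the synopsis.*

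The alternative to the last line is to correct the protocol and synopsis themselves, which under Protocol 11.1 needs a written amendment or administrative change. The SAP line avoids that.

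The cost is two or three sentences and a less favourable stated power for 0.6 points. There are no extra patients, and the sample size, tests and decision rules are unchanged.
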